9.1.2. Time to Clinical Improvement

TTCI will be evaluated by a multicomponent improvement score including WHO FC and 6MWT measurements: a > 10% increase in 6MWD or 30 meters AND an improvement to or maintenance of WHO FC II symptomatology, in the absence of a deterioration in clinical condition or death during the 24 weeks of the Main Study.

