7.4.2. Time to Clinical Worsening (TTCW)

A clinical worsening event is defined using two definitions (a composite endpoint):

Protocol Definition

1. Death from any cause
2. Hospitalization for worsening PAH (any hospitalization for worsening PAH, lung or heart and lung transplantation, atrial septostomy, or initiation of parenteral prostanoid)
3. Disease progression, defined as a decrease of more than 15% from baseline in the 6MWD combined with WHO FC III or IV symptoms at 2 consecutive visits separated by at least 14 days. The time of disease progression is at the time of initial visit.

Additional Definition

1. Death from any cause
2. Hospitalization for worsening PAH (any hospitalization for worsening PAH, lung or heart and lung transplantation, atrial septostomy, or initiation of parenteral prostanoid therapy)

3. Disease progression defined as a decrease of more than 15% from Baseline in the 6-minute walk distance (6MWD) (2 consecutive visits separated by at least 14 days), combined with World Health Organization (WHO) Functional Class (FC) III or IV symptoms at 2 consecutive visits separated by at least 14 days. Also requires the absence of a clinical rationale (e.g., an intercurrent event that would be expected to worsen the walk and functional class independent of pulmonary hypertension progression).
4. Addition of parenteral prostanoid therapy or increase of greater than 10% of any prostanoid
5. Appearance of worsening signs and symptoms of right heart failure

TTCW will be adjudicated separately for each definition of clinical worsening. TTCW is defined as the first occurrence of any of the above events (separately for each definition).

The CEAC adjudicated CWEs include the date and reason will be incorporated into the clinical database. Adjudicated TTCW is defined as the number of days from randomization date to the date of the first adjudicated CWE. Subjects who do not have an adjudicated CWE during the 24 weeks of the main study will be censored at the first OLE dose date if enrolled into OLE or if not enrolled into OLE, the minimum of last dose of study drug + 30 days or date of last contact in the main study.

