Sensitivity analysis for TTCW will be performed based on investigator assessed CWE. Investigator assessed TTCW is defined as the number of days from randomization date to the first investigator assessed CWE. Subjects who do not have an investigator assessed CWE during the 24 weeks of the main study will be censored at the date of last contact in the main study.

For a subject with CWE (adjudicated or investigator assessed) due to disease progression and the initial assessment was on-treatment during the main study, and the confirmation assessment was off treatment or post Week 24, the subject will be counted as on-treatment CWE for the main study. The date of CW is the date of the initial assessment.

The time from randomization to the adjudicated clinical worsening event will be summarized using Kaplan-Meier estimates and compared between each active treatment and placebo treatment group using the stratified log-rank test stratified by the randomization strata. Kaplan-Meier (KM) estimates of the survival distributions of the time-to-event will be tabulated and graphed by treatment group. The tabulation will include the KM estimate of the medians, 25th and 75th quartiles, and corresponding 95% CIs, if they can be estimated. The tabular and graphical summaries will include the at-risk counts for every visit. The number and percent of subjects censored, reason for censoring, and with events will be presented overall and for each visit, using last day of the visit window by treatment group. The hazard ratio and 95% CI a will be determined based on the semi-parametric Cox regression model stratified by randomization strata to estimate the magnitude of the effect. In order to test assess the effects of the stratification factors, the unadjusted/not stratified hazard ratio with associated 95% CI will be presented. KM plots will also be presented for each stratification factor by treatment group.

Sensitivity analysis on TTCW will be performed based on investigator reported clinical worsening.

The CEACP adjudicated and investigator reported CWE data will be listed.

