7.4.6. Time to Clinical Improvement (TTCI)

Subjects are considered as having clinical improvement on-treatment during the 24 weeks of the main study if they meet the following criteria:

- 10% increase in 6MWD or 30 meters increase AND
- improvement to WHO FC II or I, or maintenance of WHO FC II
- absence of a deterioration in clinical condition or death (defined as without an adjudicated clinical worsening event during the 24 weeks [see [Section 7.4.2](#)])

On-treatment is defined as randomization date through last dose of study drug + 30 days. TTCI is the number of days from the randomization date to the minimum of (date of the first assessment of 6MWD increase of 10% or 30 meters, first date improved WHO FC, last post-baseline date WHO FC II was maintained from baseline, censor date from an adjudicated TTCW). Subjects who do not improve during the 24 weeks of the main study will be censored at the first OLE dose date if enrolled into OLE or if not enrolled into OLE, the minimum of last dose of study drug + 30 days or date of last contact in the main study.

TTCI will be summarized using the same methods as specified above in [Section 7.4.2](#).

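### SAP 7.4.6 censors TTCI patients who die, or who worsen and leave, although the definition makes them certain non-improvers, so the Kaplan-Meier curve overstates improvement

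*Protocol*

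**What the plan says.** Protocol 9.1.2 requires a gain in walk distance together with functional class II reached or kept, "in the absence of a deterioration in clinical condition or death during the 24 weeks of the Main Study". SAP 7.4.6 repeats the condition and makes it operational: "absence of a deterioration in clinical condition or death (defined as without an adjudicated clinical worsening event during the 24 weeks". The first component of both worsening definitions in SAP 7.4.2 is "Death from any cause".

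Censoring is also set in SAP 7.4.6. "Subjects who do not improve during the 24 weeks of the main study will be censored at the first OLE dose date if enrolled" in the OLE; for everyone else the date is "the minimum of last dose of study drug + 30 days or date of last contact in the main study". Deaths and CWEs are not excepted.

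For the analysis, "TTCI will be summarized using the same methods as specified above in" SAP 7.4.2. There, time to worsening "will be summarized using Kaplan-Meier estimates and compared between each active treatment and placebo treatment group using the stratified log-rank test", with a stratified Cox model for the hazard ratio. Neither document mentions a competing-risk method for TTCI.

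**The concern.** Kaplan-Meier gives a censored patient the same later chance of the event as those still at risk. That suits a patient who moves away. It does not suit one who has died, or who already has an adjudicated CWE, because the endpoint's own rule fixes that patient's outcome as not improved.

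The rule bites on patients who do not reach Week 24 on drug. The schedule of assessments bars patients who do not complete Week 24 from the OLE, so early deaths and early leavers fall under the exit rule. A worsened patient who stops drug can also be dropped at last dose plus 30 days while still attending visits, which the schedule asks such patients to do.

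At stake is a benefit endpoint whose curve is raised by bad outcomes, and raised most in the arm that has more of them.

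**Working it through.** The documents state no event rate, power or sample size for TTCI, so there is no TTCI figure to reproduce. The improvement and exit rates below are assumptions. The arm size of 30 and the target days 29, 85 and 169 come from SAP 3 and Table 5. Improvement is taken as joint improvement at a visit.

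**1. Can the existing wording protect these patients?** The TTCI date in SAP 7.4.6 is a minimum that includes the censor date from adjudicated TTCW. A patient with a CWE has a TTCW event and therefore no such censor date, so this does not help.

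**2. One arm, by hand.** Take 30 patients with 12 improvers, four at each visit; true incidence is 12/30 = 40.0%. Let k of the 18 non-improvers die, or worsen and leave.

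- Exit at Day 60: S = (26/30) × (22−k)/(26−k) × (18−k)/(22−k) = (26/30) × (18−k)/(26−k)
- Exit at Day 20: S = (18−k)/(30−k)
- Exit at Day 130: S = (22/30) × (18−k)/(22−k)

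| k | 1−KM, Day 20 | Day 60 | Day 130 |
|---|---|---|---|
| 0 | 40.0% | 40.0% | 40.0% |
| 1 | 41.4% | 41.1% | 40.6% |
| 3 | 44.4% | 43.5% | 42.1% |
| 6 | 50.0% | 48.0% | 45.0% |

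If six worsened patients instead stay and are censored at Day 169, the estimate is 40.0%.

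**3. Two arms.** Assume 40% of event-free patients improve, equally at the three visits, and that exits are uniform over Days 1 to 140. The shares of exits gone before Days 29, 85 and 169 are then 0.2, 0.6 and 1. Let q be the share who die or worsen, and q′ the share who do so and leave. With a = 0.4(1−q)/3, the visit hazards are a/(1−0.2q′), a/(1−a−0.6q′) and a/(1−2a−q′).

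- All leave, q = q′ = 0.20: a = 0.1067; hazards 0.1111, 0.1379, 0.1818; 1−KM = 37.3% (true 32%).
- All leave, q = q′ = 0.05: a = 0.1267; hazards 0.1279, 0.1502, 0.1818; 1−KM = 39.4% (true 38%).
- Half leave, q = 0.20, q′ = 0.10: hazards 0.1088, 0.1280, 0.1553; 1−KM = 34.4%.
- Half leave, q = 0.05, q′ = 0.025: hazards 0.1273, 0.1476, 0.1755; 1−KM = 38.7%.

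The true deficit is 38 − 32 = 6 points. It reads as 2.1 points if every affected patient leaves, and 4.3 points if half stay.

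**4. Log-rank.** This used 4,000 simulated trials, unstratified, with true incidence 38% in both arms. With exits of 5% on placebo and 15% on active, a significant result favouring active occurs in 3.8% of trials, against 2.8% when these patients stay in the risk set. With 5% and 25% exits it is 6.7% against 2.6%.

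**5. Which common day?** Holding these patients to Day 169 is not enough. The schedule allows Week 24 visits ±5 days, and OLE entrants who have not improved are censored on their own first OLE dose date. With visits so spread, 20% exits and completing non-improvers censored on their visit day, a Day 169 rule gives about 54% against a true 32%. A small case shows why. In step 2 with k = 0, split the Week 24 visits equally between Days 167 and 171 (two improvers and nine non-improvers on each). Then S = (22/30) × (20/22) × (9/11) = 0.545, so 1−KM = 45.5% against 40.0%, with no deaths or worsening at all. Since there are no competing events here, the cumulative incidence estimator gives the same 45.5%. Closing out all completing non-improvers on one common day removes the effect.

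**The case against.** A reader might infer that the rule erases most of a real deficit, biases the hazard ratio, and so hides harm. The documents do not support going that far.

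- **Size.** Losing about two-thirds of the deficit requires every worsening event to end participation. Worsening of PAH is not a listed mandatory stopping criterion in protocol 8.1. With half staying, the loss is (6 − 4.3)/6, or about 30%. Exit rates of 20% against 5% are themselves only an assumption. The standard error of a difference between two 30-patient arms near 40% is √(2 × 0.4 × 0.6/30) = 12.6 points, larger than any of these shifts.
- **Hazard ratio.** The log-rank and Cox results remain valid cause-specific comparisons. They answer a different question from improvement as protocol 9.1.2 defines it; no bias in the hazard ratio itself was computed. Step 4 measures them against equal incidence as defined, and the effect is small unless exits differ strongly between arms.
- **Hidden harm.** Adjudicated worsening has its own analysis in SAP 7.4.2, and all-cause mortality is a separate endpoint in SAP Table 1. SAP 7.4.2 also tabulates events, censoring and censoring reasons by arm. Carried over to TTCI, this would show the crude proportion improved beside the curve.
- **Priority.** TTCI is exploratory, and Type 1 error control covers only the primary endpoint.

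All of this stands, and it limits the consequence. It does not remove the mismatch between the definition and the censoring rule.

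**Conclusion.** The point holds in a limited form. For patients who die, or who worsen and leave or stop drug before Week 24, SAP 7.4.6 assigns a future chance of improvement that its own definition rules out. The Kaplan-Meier curve therefore overstates cumulative improvement, more so in the arm with more such exits. Under the assumed 12 improvers in 30, the excess is roughly 1 point per exit: 0.6 to 1.4 points for one, 2.1 to 4.4 for three and 5.0 to 10.0 for six, depending on timing. Worsened patients who complete Week 24 add no such bias. The PVR conclusion is unaffected.

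**What to change.** Amend SAP 7.4.6 in one of two ways:

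- Treat death or adjudicated CWE as a competing event, and report cumulative incidence in place of 1−KM.
- Or keep these patients in the risk set as non-improvers to Day 182, the end of the Week 24 window for walk distance and functional class in SAP Table 5.

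Under either option, censor non-improvers who complete Week 24 on one common day (Day 182), or set all times to nominal visits; step 5 shows why. State which of the two SAP 7.4.2 worsening definitions applies. Make explicit that a patient who meets the walk and class criteria and later has a CWE within 24 weeks is a non-improver. Keep the present censoring for patients who leave for other reasons. Report the proportion improved by Week 24 in each arm.

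While editing, also reconcile the TTCI date, which is a minimum of component dates although the criteria must be met jointly. That is a separate matter.

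The cost is a short SAP edit and slightly more programming, with no new data. The reported improvement rate will be somewhat lower.

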9.1.3. Time to Clinical Worsening

TTCW is defined as the first occurrence of a composite end point of: 1. Death from any cause, 2. Hospitalization for worsening PAH (any hospitalization for worsening PAH, lung or heart and lung transplantation, atrial septostomy, or initiation of parenteral prostanoid therapy), 3. Disease progression defined as a decrease of more than 15% from baseline in the 6MWD combined with WHO FC III or IV symptoms at 2 consecutive visits separated by at least 14 days (adjudicated).

9.1.4. Six-Minute Walk Test/Six-Minute Walk Distance

The 6MWT is a simple, commonly used, standardized measure of functional exercise capacity and endurance. It is a commonly used measure of efficacy in PAH clinical studies. The change from baseline in 6MWD following intervention indicates symptomatic improvement over that time-period. Improvement in 6MWD has been correlated with improvements in quality of life. Refer to Appendix 6.

9.1.5. Echocardiography

Patients will undergo resting cardiac echocardiography at specified visits. Echocardiographic endpoints will include right atrial size and measures of RV function (TAPSE, tricuspid annular systolic velocity, and RV fractional area change). There will be a core imaging laboratory for centralized blinded adjudication of the echocardiographic endpoints.

Full details available in echocardiograph manual.

9.1.6. Pulmonary Function Tests (PFTs)

PFTs (performed with or without bronchodilation) should be completed at Screening if there are no historical results from tests completed within 24 weeks prior to Screening.

9.1.7. World Health Organization Functional Class

PAH functional disease severity is classified according to WHO FC. Patients are classified into 1 of 4 functional classes on the basis of their degree of physical limitation and associated symptoms. Refer to Appendix 7 for full description of each Functional Class.

Protocol RVT-1201-2002

Effective: 19JAN2022

9.1.8. N-terminal pro-Brain Natriuretic Peptide Level

NT-proBNP is a strong predictor of disease progression and mortality in PAH patients. Current PAH treatment guidelines recommend measurement of NT-proBNP levels for both risk assessment and longitudinal follow up. NT-proBNP levels are also a good marker of response to treatment.

9.1.9. Pulmonary Arterial Hypertension-Symptoms and Impact Questionnaire

The PAH SYMPACT Questionnaire is the first instrument for quantifying PAH symptoms and impacts. It is a brief, disease-specific patient-reported outcome (PRO) instrument possessing good psychometric properties.

The questionnaire consists of two parts:

- Day 1 to Day 6: The Questionnaire asks 13 questions regarding the patient's PAH symptoms for the past 24 hours. The patient is required to complete these questions each day for Days 1 to 6.
- Day 7: The Questionnaire asks 12 questions regarding the patient's PAH symptoms for the past 24 hours and an additional 11 questions about the "Impacts" that best describes how the patient's life was affected by PAH.

Prior to departing the study site at the Screening Visit, patients will be instructed and trained on how to complete the questionnaire. Patients will start the PAH-SYMPACT questionnaire 6 days prior to the visit for which PAH-SYMPACT is collected, with the Day 7 being completed on the day of the visit.

An example of the PAH SYMPACT Questionnaire can be found in Appendix 9.

9.1.10. Registry to Evaluate Early and Long-term Pulmonary Arterial Hypertension Disease Management Lite 2 Risk Assessment Calculator

REVEAL Lite 2 includes 6 non-invasive variables: FC, vital signs (SBP and HR), 6MWD, NT-proBNP, and renal insufficiency (by eGFR). REVEAL Lite 2 will be a calculated parameter (by statistician) at Baseline and Week 24 of the Main Study and Week 24 of the OLE (this calculation will not be in the eCRF).

9.1.11. Actigraphy

Data on physical activity will be collected using a small wrist-worn physical activity tracker (monitor designed for documenting physical movement) that will transmit all activity through the 24 weeks of the Main Study.

9.2. Safety Assessments

9.2.1. Pregnancy Testing

Serum pregnancy tests will be obtained for all female patients of childbearing potential at Screening and every 4 weeks while on IP. Urine pregnancy tests will be obtained at all subsequent visits and must be confirmed negative at the Baseline Visit before randomization and IP dispensation. Additional pregnancy tests should be completed anytime menstruation is delayed and in women with infrequent or irregular menstrual cycles. A positive urine test will be confirmed by a serum test.

Serum pregnancy test and FSH levels will be obtained at the Screening Visit for any postmenopausal women with amenorrhea for < 2 years to confirm FSH level (must be > 35 IU/mL). If FSH value is confirmed as postmenopausal at Screening, no further pregnancy tests are required. If level does not confirm postmenopausal status, urine pregnancy tests will be required at all scheduled visits and patients must agree to use an approved method of highly effective contraception (refer to Section 5.4.1).

Planned time points for all safety assessments are provided in the SoA (Section 1.3, Section 1.4, and Section 1.5).

9.2.2. Physical Examinations

A complete physical examination will include, at a minimum, assessments of the cardiovascular, respiratory, gastrointestinal and neurological systems. Height (only at Screening) and weight will also be measured and recorded.

Investigators should pay special attention to clinical signs related to previous serious illnesses.

9.2.3. Vital Signs

Vital signs will be measured after 5 minutes rest and will include temperature, systolic and diastolic blood pressure, respiration rate and oxygen saturation.

9.2.4. Electrocardiograms

Three 12-lead ECGs, one minute apart, will be obtained after at least 5 minutes of rest at Baseline. Single 12-lead ECGs will be performed at all other time points.

Each ECG performed during the study will be obtained using an ECG machine that automatically calculates the HR and measures PR, QRS, QT and QTcF intervals.

The corrected QT interval (QTc) using Fridericia's formula (QTcF) will be used for each individual patient to determine study eligibility and for all on-study ECGs. The QTcF interval will be based on the ECG machine's algorithm.

Clinically significant ECG findings that are present prior to initiation of IP, if not exclusionary, must be documented in the Medical History section of the eCRF. Any clinically significant abnormality that represents a change from baseline will be reported as an AE and followed until resolution.

9.2.5. Clinical Safety Laboratory Assessments

A central laboratory will be used for clinical safety laboratory assessments. The details for sample collection, preparation, and shipping to the central laboratory will be provided in a separate lab manual. Reference ranges for all safety parameters will be provided to the site by the central laboratory responsible for the assessments.

See the SoA (Section 1.3, Section 1.4, and Section 1.5) for timing and frequency.

Hematology, clinical chemistry, coagulation, urinalysis, and additional parameters to be tested are listed below:

9.2.5.1. Hematology

Hematology Panel			
Platelet Count	Red Blood Cell (RBC) Indices:	Automated WBC	
		Differential:	
RBC Count	Mean Corpuscular Volume	Neutrophils	
	(MCV)		
White Blood Cell (WBC)	Mean Corpuscular Hemoglobin	Lymphocytes	
Count (Absolute)	(MCH)		
Reticulocyte Count	Mean Corpuscular Hemoglobin	Monocytes	
	Concentration (MCHC)		
Hemoglobin	Eosinophils	Basophils	
Hematocrit			

9.2.5.2. Coagulation

Coagulation Panel	
Prothrombin Time (PT)	
INR	
Activated Partial Thromboplastin Time (aPTT)	

Coagulation testing will be done at Screening, Week 12, and Week 24 for all patients on the Main Study and at Weeks 12 and 24 during the OLE in the first 24 weeks and every clinic visit post 24 weeks in the OLE. In addition, coagulation will be done at an unscheduled visit if there is an ALT result \geq 3X ULN at any study visits. Refer to Appendix 3.

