4.4.1.2. Aminotransferase (Alanine aminotransferase or Aspartate Aminotransferase) Elevation

Management recommendations for ALT or AST elevations are based on U.S. Food and Drug Administration (FDA) Guidance for Liver Toxicity.

In general, all baseline or treatment-emergent ALT or AST elevations > 3X ULN should be confirmed within 48 to 72 hours with repeat assessments of ALT and AST as well as TBL, alkaline phosphatase (ALP), prothrombin time/INR, and complete blood count for eosinophil levels. Further details for managing IP reduction, restart, and discontinuation can be found in Appendix 3.

If at any time, the criteria as outlined in Section 8 are met, the IP must be permanently discontinued.

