8.1. Discontinuation of Investigational Product

The Medical Monitor should be notified of any change to background PAH therapy to determine any need for withdrawal. See Section 8.2 for study withdrawal procedures.

Patients meeting any of the following liver chemistry criteria must be withdrawn (IP should be discontinued immediately) from the study by the Investigator:

- ALT or AST > 3X ULN and TBL > 1.5X ULN or INR > 1.5
- ALT or AST > 3X ULN with the appearance of fatigue, nausea, vomiting, right upper quadrant pain or tenderness, fever, rash, and/or eosinophilia (> 5%)
- ALT or AST > 5X ULN for more than 2 weeks
- ALT or AST >8X ULN

If liver chemistry tests meet any of the above criteria, repeat testing should be performed within 48 to 72 hours and the patient followed until resolution.

Patients meeting any of the following confirmed QT/QTc-related criteria must be withdrawn from the study by the Investigator:

- QTcF interval > 500 ms
- QTcF interval > 480 ms AND increase from Baseline ≥ 60 ms
- QTcF interval > 480 ms associated with syncope, life-threatening arrhythmias, resuscitated cardiac arrest, or seizure

The Investigator must also discontinue/withdraw a patient's participation in the study if any of the following criteria apply:

- Pregnancy
- Significant protocol violation/lack of compliance with the study and/or study procedures non-compliance with IP for discontinuation of patient is defined as < 50%.
- Severe constipation (e.g., obstipation with manual evacuation indicated) and/or severe, persistent, or worsening abdominal pain
- Any significant worsening on postdose C-SSRS indicative of active suicidal ideation with intent to act (defined as C-SSRS Suicidal Ideation category score of 4 or 5) or behavior (either preparatory acts/behavior, aborted attempt, interrupted attempt, or actual attempt)
- Severe depression or anxiety based on a HADS Depression or Anxiety score ≥ 15, or a QIDS-C Total Score ≥ 16.

• Any severe psychiatric or CNS AE as determined by the Investigator.

The Investigator may discontinue/withdraw a study patient's participation in the study if any of the following criteria apply:

Protocol RVT-1201-2002

Effective: 19JAN2022

• Behavioral or administrative reason

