APPENDIX 3. LIVER SAFETY: SUGGESTED ACTIONS AND FOLLOW-UP ASSESSMENTS

Protocol RVT-1201-2002

CTCAE Grade	Description	IP	Symptom/treatment
Mild = 1	AST or ALT > 1.5X ULN < 3X ULN	Continue as planned	No action taken
Moderate = 2	AST or ALT ≥ 3X ULN and < 5X ULN and no signs of severe liver damage	Reduce to one pill BID or interrupt treatment (to be decided by Investigator, based on individual risk assessment.)	Re-test ALT and AST, as well as ALP, TBL, and eosinophils within 48-72 hours, then at ~7 days, then at ~2 weeks, and assess for signs of severe liver damage: If AST and ALT < 3X ULN after 2 weeks, return to initial dose if reduced, restart at reduced dose if interrupted. Monitor labs (see above) every 2 weeks for at least 8 weeks. If AST and ALT ≥ 3X ULN after 2 weeks or anytime thereafter, permanently discontinue study medication.
Severe = 3	AST or ALT increase to ≥ 5X ULN and < 8X ULN and no signs of severe liver damage	Interrupt treatment	Re-test ALT and AST, as well as ALP, TBL, and eosinophils within 48-72 hours, then at ~7 days, then at ~2 weeks, and assess for signs of severe liver damage: • If AST and ALT < 3X ULN after 2 weeks, restart at reduced dose. Monitor labs (see above) every week for 4 weeks, then

Protocol RVT-1201-2002 Effective: 19JAN2022

CTCAE Grade	Description	IP	Symptom/treatment
			every 2 weeks for at least 8 weeks.
			• If AST and ALT ≥ 3X ULN after 2 weeks or anytime thereafter, permanently discontinue study medication.
Life-threatening = 4	AST or ALT increase to ≥ 8X ULN or signs of severe liver damage:	Permanently Discontinue	Patients showing these laboratory abnormalities need to be followed up
	-Increase of liver transaminases (ALT or AST ≥ 3X ULN)		closely
	and		
	Appearance of fatigue, nausea, vomiting, right upper abdominal quadrant pain or tenderness, fever, rash and/or eosinophilia (> 5%)		
	or		
	TBL > 1.5X ULN		
	or		
	INR > 1.5		

Abbreviations: ALP = alkaline phosphatase; ALT = alanine aminotransferase; AST = aspartate aminotransferase; BID = twice daily; CTCAE = Common Terminology Criteria for Adverse Events; INR = international normalized ratio; IP = investigational product; ULN = upper limit of normal

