8.3.4. Evaluation of Labs of Special Interest

Liver enzymes (ALT, AST, GGT, ALP) will be evaluated in terms of upper limits of normal (ULN). The result will be divided by the ULN, and summarized using descriptive statistics. In addition, the number and percentage of subjects with GGT or ALP increases $>2\times$, $3\times$, $5\times$, $8\times$, $10\times$, $15\times$, and $20\times$ ULN will be presented based on their maximum post-baseline value, by treatment group.

Summaries of coagulation parameters will be presented by treatment group for the subset of subjects concomitantly taking drugs included in the WHO Drug Dictionary Standardized Drug Grouping “Antithrombotic drugs”.

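### Protocol 4.4.1.2, 9.2.5.2 and Appendix 3 disagree on whether INR is measured after an aminotransferase rise, although the mandatory liver stopping rule uses it

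*Protocol*

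**What the plan says.** **The stopping rule.** Protocol 8.1 lists liver criteria under which patients "must be withdrawn (IP should be discontinued immediately) from the study by the Investigator". The first criterion reads "ALT or AST > 3X ULN and TBL > 1.5X ULN or INR > 1.5". The rule also appears in the Section 2.3 risk table and, as the definition of severe liver damage, in the Grade 4 row of Appendix 3.

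**Follow-up testing.** Three places give instructions:

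- Section 4.4.1.2 says that, in general, any ALT or AST above 3 times ULN should be confirmed in 48 to 72 hours, with "repeat assessments of ALT and AST as well as TBL, alkaline phosphatase (ALP), prothrombin time/INR" and a blood count for eosinophils. It refers to Appendix 3 for management of study drug.
- Section 9.2.5.2 sets the coagulation schedule and continues: "In addition, coagulation will be done at an unscheduled visit if there is an ALT result" at or above 3 times ULN. AST is not named. It also refers to Appendix 3.
- Appendix 3, in both the Grade 2 and Grade 3 rows, says "Re-test ALT and AST, as well as ALP, TBL, and eosinophils within 48-72 hours", repeated at about 7 days and 2 weeks. The same cells tell the site to "assess for signs of severe liver damage".

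**Routine schedule.** The main-study schedule has safety laboratories at Weeks 4, 8, 12, 18 and 24. Its footnote limits coagulation to Screening and Weeks 12 and 24.

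**Anticoagulation.** Appendix 1 lists dabigatran among drugs allowed with monitoring. SAP Table 13 grades INR against the patient's baseline when the patient is anticoagulated. SAP 8.3.4 adds: "Summaries of coagulation parameters will be presented by treatment group for the subset of subjects concomitantly taking drugs" in the antithrombotic grouping.

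**The concern.** A mandatory stopping rule needs its inputs to be collected whenever it could apply. This rule covers either enzyme and uses INR, but two of the three testing instructions do not order an INR when AST alone rises, and one does not order it for any rise.

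INR also decides which row of Appendix 3 applies. Grades 2 and 3 lead to dose reduction or interruption, with a possible return to treatment. Grade 4 leads to permanent discontinuation. A site without an INR cannot fully exclude Grade 4. Liver enzyme elevation is a declared adverse event of special interest, so sites could handle the same laboratory picture differently in an area that the trial is meant to watch closely.

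**Working it through.** No figure in the plan needs reproducing. The check sets the passages side by side and counts.

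**1. Is INR ordered after an enzyme rise?**

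| Source | Trigger | INR after ALT rise | INR after AST-only rise |
|---|---|---|---|
| 4.4.1.2 | ALT or AST, > 3X ULN | yes | yes |
| 9.2.5.2 | ALT, ≥ 3X ULN | yes | no |
| Appendix 3, Grades 2 and 3 | ALT or AST, ≥ 3X ULN | no | no |

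INR is named in 2 of 3 instructions for an ALT rise and in 1 of 3 for an AST-only rise. Comparing the panels item by item, 4.4.1.2 has ALT, AST, TBL, ALP, PT/INR and eosinophils. Appendix 3 has ALT, AST, ALP, TBL and eosinophils. PT/INR is the only item lost.

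**2. Does the routine schedule fill the gap?** On-treatment laboratory visits are Weeks 4, 8, 12, 18 and 24, and coagulation is drawn at Weeks 12 and 24. So 5 − 2 = 3 of 5 visits have no routine INR. The wait to the next scheduled INR is:

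- from Week 4: 12 − 4 = 8 weeks
- from Week 8: 12 − 8 = 4 weeks
- from Week 18: 24 − 18 = 6 weeks

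Each is far longer than the 48 to 72 hours in 4.4.1.2. The first 24 weeks of the open-label extension have the same laboratory weeks and the same two coagulation weeks, so the count there is also 3 of 5.

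**3. Illustration (values assumed for the example).** At Week 8 a patient has AST at 4 times ULN, with normal ALT and bilirubin and no symptoms. Under 4.4.1.2 an INR is drawn within 72 hours. Under 9.2.5.2 nothing is triggered. Under Appendix 3 the retest has no INR, yet the choice between Grade 2 and Grade 4 now depends on INR alone.

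**4. Are the statements of the stopping rule the same?**

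| Source | Enzyme limit | Bilirubin limit | INR limit | Anticoagulation provision |
|---|---|---|---|---|
| 2.3 | > 3X ULN | > 2X ULN | > 1.5 | none |
| 8.1 | > 3X ULN | > 1.5X ULN | > 1.5 | none |
| Appendix 3, Grade 4 | ≥ 3X ULN | > 1.5X ULN | > 1.5 | none |

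The bilirubin limit and the enzyme boundary differ. In 8.1 the terms are joined by an unbracketed and/or sequence, so the text alone does not show whether INR is an alternative to bilirubin or stands by itself. None of the 3 statements provides for anticoagulated patients, whereas the SAP treats such patients separately in 2 places (Table 13 and 8.3.4).

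**The case against.** The strongest reply is that 4.4.1.2 already closes the gap. Its enzymes and its threshold match 8.1 and it names PT/INR, so an AST-only rise does call for the test. The sentence in 9.2.5.2 is worded as an addition and need not restrict anything. Section 4.4.1.2 sends sites to Appendix 3 for study-drug decisions, not for a substitute panel. Unscheduled tests are allowed at any time, and a laboratory manual that is not among these documents may already contain the instruction. The other liver criteria in 8.1 do not need INR, and Appendix 3 stops treatment in any case if the enzymes stay at or above 3 times ULN after two weeks.

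Most of this stands, and it limits the point. It does not remove it. Section 4.4.1.2 is phrased as a general recommendation, discretionary testing is weaker than a mandatory rule, and both 4.4.1.2 and 9.2.5.2 lead the site to a table whose retest list lacks INR.

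Four stronger readings may tempt a reader, and the documents do not support them:

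- *The stopping rule cannot be applied.* It can, by following 4.4.1.2.
- *Anticoagulated patients are nowhere separated.* The SAP separates them for grading and for summaries. Only the protocol's stopping-rule statements do not. A uniform stopping limit and a baseline-relative grade serve different purposes and can coexist, so the difference is not in itself an error.
- *An anticoagulated patient is stopped on INR alone.* Section 2.3 brackets INR with bilirubin, and Appendix 3 places INR under an enzyme rise to at least 3 times ULN.
- *The primary analysis is affected.* The tolerability imputation in SAP 7.1.2.2 applies only to a missed assessment. Protocol 8.2.1 keeps consenting patients in visits to Week 24 and seeks a catheterization after at least 12 weeks of treatment. SAP Table 4 accepts one from Day 2 to Day 197. The documents give no frequency for AST-only rises or anticoagulation, so this consequence would be speculation.

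**Conclusion.** The concern holds as an inconsistency in the protocol's liver follow-up instructions. INR is ordered by one of three instructions after an AST-only rise and by two of three after an ALT rise. Three of five on-treatment laboratory visits have no routine INR to fall back on. The exposed case is a site that relies on 9.2.5.2 or Appendix 3 alone after an AST-only rise, or on Appendix 3 alone after any rise. That site may lack a result used by 8.1 and by the Appendix 3 grading.

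How often this would happen cannot be estimated. The one liver figure in the protocol is mild, transient ALT elevation in 5 of 136 healthy subjects, which says nothing about AST-only rises in patients with PAH. The conclusion assumes that no laboratory manual already orders the INR. The differing stopping-rule statements are a separate contradiction to settle at the same time. The anticoagulation point is a question for the sponsor, not a finding of error. This should be corrected because it concerns a mandatory safety rule.

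**What to change.** Reconcile 4.4.1.2, 9.2.5.2 and Appendix 3 so that they state the same enzyme trigger and the same retest panel, and so that the panel supplies every result that 8.1 and Appendix 3 use.

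In the same edit:

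- Reconcile the statements of the stopping rule in 2.3, 8.1 and Appendix 3: the bilirubin limit (2 versus 1.5 times ULN), the enzyme boundary (above 3 versus at or above 3 times ULN, which also differs between the testing triggers), and the grouping of the and/or terms in 8.1.
- Have the hepatic-safety lead state whether the absolute INR limit in the stopping rule is meant to apply unchanged to anticoagulated patients, given that SAP Table 13 grades their INR against baseline.

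Which limits and which trigger are right is for the sponsor's clinical team. This point asks only that the passages agree.

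The cost is wording in four protocol places (2.3, 4.4.1.2 and 8.1 or 9.2.5.2 as needed, and Appendix 3), with a matching line in the laboratory manual if it lacks one. The coagulation panel already includes PT and INR, so no new assay is needed.
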